7.5 Efficacy

Except where indicated, for the Dose Evaluation Phase, efficacy parameters will be summarized by cohort using the All Dose Evaluation Excluding DLT Treated Subjects population.

For the Dose Expansion Phase, efficacy parameters will be summarized by cohort using the All 2-stage Treated Subjects population.

Supportive listing will be provided for response, time to response, duration of response, PFS and OS.

7.5.1 Objective Response Rate

BOR will be summarized by response category and ORR will be computed along with an exact 90% CI (primary analysis for ORR as primary endpoint, see [Section 4](#)).

The primary population for estimating the ORR will be the All Dose Evaluation Excluding DLT Treated Subjects population. Additionally, the parameters will be summarized using the All Dose Evaluation Treated Subjects population (supportive analyses). All analyses will be presented as-treated.

For the Dose Evaluation Phase, the decision to further study ulocuplumab combined with nivolumab in each tumor type will primarily be based on the pre-defined Simon 2-stage design thresholds (at least 4 responders for SCLC and at least 2 responders for PAC), using data from the IA. In addition, the selection of the recommended dose will be based on all available safety and efficacy data from both tumor types. The decision to proceed from the Dose Evaluation Phase to the Dose Expansion Phase will be conducted for each tumor type independently. Consideration may be given for evaluating final data before decision is reached to stop further study of the combination to ensure that the full characterization of the response pattern is evaluated.

The decision to proceed with an open label randomized two-arm Phase 2 design rather than completing the second stage of a Simon 2-stage design for the Expansion Phase will be taken if, among the treated subjects in the recommended dose selected during the Dose Evaluation Phase, a “high” frequency of responders is observed. For SCLC, this “high” number will be at least 9 responders and, for PAC, at least 6 responders. This number of responders has been defined considering clinical input but, ensuring that the related proportion of responders also presents with a 90% exact CI lower limit above 25% for SCLC or above 12% for PAC. These percentages correspond to the minimum proportion of responders that would be needed at the end of a Simon 2-stage design in order to further evaluate the drug (for SCLC, 11 responders among the 44 subjects is 25% and, for PAC, 5 responders among the 41 subjects is 12%).

For the Dose Expansion Phase, the primary population will be the All 2-stage Treated Subjects population (as-treated analyses).

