5.1 SCLC Sample Size

For SCLC, up to approximately 175 treated subjects may be needed. This sample size considers the following:

- Up to 18 subjects for the DLT evaluation
- 19 subjects per cohort for the Dose Evaluation Phase (57 subjects for three randomized cohorts)
- A second stage of a Simon 2-stage like design in the Dose Expansion Phase that would require an additional 25 subjects

OR

- A randomized Phase 2 study with comparative arm in the Dose Expansion Phase that would require an additional 50 subjects per arm (i.e. 100 for the two arms)

These numbers are obtained using the following methods and assumptions:

- A Simon optimal 2-stage design will test the null hypothesis that the true response rate is less than or equal to 15% versus the alternative hypothesis that it exceeds 15%. The type I error rate will be 5% (one-sided) and the design will have 90% power to reject the null hypothesis when the true response rate is 35%. The Simon design in this tumor type will require 19 treated subjects for the first stage and at least 4 responders to initiate Stage 2. An additional 25 treated subjects will be needed for the second stage and the drug will be considered of potential clinical interest if, at the end of the second stage, there are 11 or more responders out of the total of 44 treated subjects. Subjects who were assigned treatment but never treated will not count towards the total of 19 treated subjects for the first stage or the 44 treated subjects in a cohort and will be replaced.
- If an open label randomized Phase 2 with comparative arm study is initiated (1:1 ratio), the primary measurement for efficacy will be IRRC assessed ORR. Considering one-sided alpha level of 0.10 a sample size of 50 subjects per arm would provide approximately 80% power to detect a difference of 20% in the response rates between the two arms (based on a Fisher's exact test) assuming an ORR of 35% for the combination arm of ulocuplumab plus nivolumab and an ORR of 15% for the nivolumab monotherapy arm.

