6.3 Populations for Analyses

All populations will be defined separately by tumor type.

- Dose Evaluation Phase:
 - All DLT-evaluable Subjects: All subjects who completed the DLT evaluation period (i.e., received at least 5 out of 6 doses of ulocuplumab and at least 2 out of 3 doses of nivolumab in a 6 week dosing period or experienced a DLT).
 - All Dose Evaluation Enrolled Subjects: All subjects who signed an informed consent form and were registered into the IVRS during the Dose Evaluation Phase (this population includes subjects from the DLT evaluation period).
 - All Dose Evaluation Treated Subjects: All subjects who received at least one dose of any study medication during the Dose Evaluation Phase (this population includes subjects from the DLT evaluation period).
 - All Dose Evaluation Excluding DLT Treated Subjects: All subjects who were allocated to a unique cohort during the Dose Evaluation Phase and were treated (this population excludes subjects from the DLT evaluation period).
- Dose Expansion Phase:
 - All Dose Expansion Enrolled Subjects: All subjects who signed an informed consent form and were registered into the IVRS during the Dose Expansion Phase.
 - All Dose Expansion Treated Subjects: All subjects who were allocated to a unique cohort during the Dose Expansion Phase and were treated (this population correspond to the second stage of a 2-stage design and it will not be used as such for reporting, see “Both Phases combined” below).
- Both Phases combined:
 - All 2-stage Enrolled Subjects: This population consists of the pooling of the “All Dose Evaluation Enrolled Subjects” with the “All Dose Expansion Enrolled Subjects”.
 - All 2-stage Treated Subjects: This population consists of the pooling of the “All Dose Evaluation Excluding DLT Treated Subjects” with the “All Dose Expansion Treated Subjects”.
 - All 2-stage Including DLT Treated Subjects: This population consists of the pooling of the “All Dose Evaluation Treated Subjects” with the “All Dose Expansion Treated Subjects”.
- Other populations (note that the PK and the immunogenicity are study drug specific as these populations are defined for ulocuplumab or for nivolumab, separately):
 - All Dose Evaluation PK Evaluable Subjects: All subjects who received at least one dose of study medication and have available serum concentration data during the Dose Evaluation Phase.

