7 STATISTICAL ANALYSES

7.1 General Methods

All analyses will be presented separately by tumor type.

Descriptive summaries of continuous and other numeric variables will at least consist of the following summary statistics: median, minimum and maximum values. Categorical variables will be summarized by the frequency and proportion of subjects falling into each category. Unless otherwise indicated, percentages in tables will be column percentages, using the total number of observations in the population, grouped by cohort, as the denominator. Percentages will be rounded to one decimal place, and thus may not always add up to exactly 100%.

AEs will be coded using the Medical Dictionary for Regulatory Activities (MedDRA), and the most recent version of the dictionary at the time of the database lock will be used. AEs and laboratory tests will be graded using the National Cancer Institute - Common Toxicity Criteria for Adverse Event (NCI-CTCAE) Version 4.03. Clinical laboratory values will be first reported in using International System of Units (SI). Analyses will be repeated using US conventional units. Medications will be coded using the most recent version of the BMS WHO Drug Dictionary.

Time-to event variables (e.g., PFS, OS, DOR, etc.) will be analyzed using the Kaplan-Meier product limit method (KM). When specified, the median will be reported along with 95% confidence interval (CI) using Brookmeyer and Crowley methodology⁴ (using the log-log transformation for construction of CI). Rates at fixed timepoints (e.g., PFS at 6 months) will be derived from the Kaplan-Meier estimate along with their corresponding log-log transformed CIs. Exact confidence intervals for binomial proportions will be derived using the Clopper-Pearson method⁵.

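### At exactly the Simon success count, the pooled 90% Clopper-Pearson interval for ORR still contains the null that the count rule rejects (small reporting conflict; decisions unaffected)

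*SAP*

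**What the plan says.** SAP 7.5.1 says "ORR will be computed along with an exact 90% CI" and calls this the "primary analysis for ORR as primary endpoint". The method comes from SAP 7.1: "Exact confidence intervals for binomial proportions will be derived using the Clopper-Pearson" method. Protocol 8.4.2.1 gives the same level and method. The Protocol Synopsis (Analyses) gives the same method at 95%.

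For the Dose Expansion Phase, SAP 7.5.1 adds that "the primary population will be the All 2-stage Treated Subjects population (as-treated analyses"). SAP 6.3 defines that population as the Stage 1 treated subjects outside the DLT period together with the Stage 2 treated subjects. Protocol 8.4.2 pools in the same way.

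Success is defined by a count. SAP 5.1 (SCLC) says "The type I error rate will be 5% (one-sided) and the design will have 90% power"; the null is 15% and the alternative 35%. Stage 2 needs at least 4 responders in 19, and the drug is of interest if "there are 11 or more responders out of the total of 44 treated subjects". SAP 5.2 (PAC) uses 5% against 20%, at least 2 in 21, then at least 5 in 41. Protocol 8.1.1 and 8.1.2 match. Neither document adjusts the pooled interval for the Stage 1 rule or says which result governs if interval and count disagree.

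**The concern.** A two-sided 90% interval leaves 5% in each tail, so readers will set it beside a one-sided 5% test and expect the two to agree. The SAP invites this: section 7.5.1 justifies its threshold for high efficacy by comparing a 90% exact lower limit with a benchmark, the "minimum proportion of responders that would be needed at the end of a Simon 2-stage design in order to further evaluate the drug".

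Clopper-Pearson on 44 or 41 subjects assumes a fixed sample. In the two-stage design, some routes to the same total are closed because the trial stops after Stage 1. The test counts only the open routes and the interval counts all of them. A tumor type that just meets its success rule could thus be reported with a primary-analysis interval that includes the rate the rule has rejected. Without advance wording, the choice of interval would be made after the data are seen.

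**Working it through.** **Inputs** (SAP 5.1, 5.2; Protocol 8.1.1, 8.1.2)
- SCLC: p0 = 0.15, p1 = 0.35, n1 = 19, continue if X1 ≥ 4, n = 44, success if total ≥ 11.
- PAC: p0 = 0.05, p1 = 0.20, n1 = 21, continue if X1 ≥ 2, n = 41, success if total ≥ 5.

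**1. The plan's own figures.** Let T(s; p) = Σ over x ≥ r1 of P(X1 = x) · P(X2 ≥ s − x). This is the probability of passing Stage 1 and reaching total s, with r1 the Stage 1 minimum and X2 binomial on the 25 or 20 added subjects.
- SCLC: T(11; 0.15) = 0.0481; T(11; 0.35) = 0.9049.
- PAC: T(5; 0.05) = 0.0457; T(5; 0.20) = 0.9017.

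The stated 5% and 90% are reproduced.

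**2. The planned interval.** Clopper-Pearson 90% limits are the 5% quantile of Beta(x, n − x + 1) and the 95% quantile of Beta(x + 1, n − x).

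| Result | Lower | Upper | Null |
|---|---|---|---|
| 11/44 | 14.70% | 37.97% | 15%, inside |
| 12/44 | 16.55% | 40.41% | 15%, outside |
| 5/41 | 4.93% | 23.95% | 5%, inside |
| 6/41 | 6.57% | 26.85% | 5%, outside |

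The gaps are 15.00 − 14.70 = 0.30 and 5.00 − 4.93 = 0.07 points. Both remain visible at the SAP's one-decimal rounding.

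**3. Why they differ.** The fixed-sample tails at the null are P(X ≥ 11 | 44, 0.15) = 0.0566 and P(X ≥ 5 | 41, 0.05) = 0.0525, both above 0.05. Routes that the Stage 1 rule closes account for 0.0566 − 0.0481 = 0.0085 and 0.0525 − 0.0457 = 0.0068.

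**4. An interval that matches the test.** With stage-wise ordering (Stage 1 stops rank below every Stage 2 result), the lower limit solves T(s; p) = 0.05 and the upper limit solves 1 − T(s + 1; p) = 0.05.
- 11/44: 15.09% to 39.43%.
- 5/41: 5.13% to 24.78%.

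Both exclude the null. For a Stage 1 stop the same equations reduce to Clopper-Pearson on 19 or 21 subjects.

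**5. How often the conflict would arise.** Probability of passing Stage 1 and ending exactly on the cut-off, without the randomized exit:
- SCLC: 4.0% at ORR 35%, 11.1% at 25%, 8.1% at 20%.
- PAC: 6.6% at ORR 20%, 13.8% at 15%, 14.2% at 10%.

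**6. Coverage given that Stage 2 was run.** The lowest value between null and alternative is 88.4% (SCLC) and 88.6% (PAC) for Clopper-Pearson, against 84.6% and 83.2% for the stage-wise interval.

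**7. The Synopsis level.** At 95%, the Clopper-Pearson lower limits are 13.19% (11/44), 14.96% (12/44), 4.08% (5/41) and 5.57% (6/41). The SCLC conflict would then extend to 12/44.

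**The case against.** The strongest reply is that nothing in the plan fails. Success is a count, no section uses the end-of-Stage-2 interval as a test, and Protocol 8.4.2.1 uses it to summarize ORR. That stands, and it limits the point to reporting.

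A second reply is that the stage-wise interval is no clear improvement. A pooled result exists only after continuation, and there its worst coverage is lower (step 6). This stands too: whole-design coverage against coverage given continuation is a choice, so replacing Clopper-Pearson outright is not warranted.

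Third, stage-wise limits need a binding rule and a Stage 1 count fixed at the interim analysis. The plan offers neither. Low efficacy only puts a tumor type on hold (SAP 2.1.2), final data may be awaited (SAP 7.5.1), and best response keeps accruing until progression or subsequent therapy (SAP 4.1.1), so Stage 1 subjects can become confirmed responders later. At ≥ 9/19 or ≥ 6/21 the tumor type moves to a randomized study, with probability 18.5% and 23.1% at the alternatives. SAP section 2 leaves out the analysis of that study, not the exit rule. These limits must be stated with the interval.

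Two stronger readings are tempting. One is that the pooled interval has a serious coverage failure. Coverage of the whole reporting procedure without the exit does fall to 88.3% (SCLC) and 88.7% (PAC), but only near ORR 36% and 21%. Much of the miss there comes from Stage 1 stops, and coverage given a pooled report is 93.0% and 93.1%. The other is that the cut-off makes up most successes: 52% (SCLC) and 68% (PAC) at the null rates. Those are false positives, for which an interval containing the null is correct.

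**Conclusion.** The conflict is real and small: 0.30 points for SCLC and 0.07 for PAC, at one count per tumor type at the 90% level. A reader might infer that type I error is inflated or that a go decision could be overturned. The documents do not support that: the count rule decides, with type I error 0.048 and 0.046 and power 0.905 and 0.902. Clopper-Pearson remains right for Stage 1-only data. What is missing is a statement of which result governs and an interval consistent with the test. Severity is optional to minor.

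The figures assume exactly 19 + 25 and 21 + 20 treated subjects, the Stage 1 rule followed on the interim count, no later Stage 1 responders, and no randomized exit.

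**What to change.** In SAP 7.5.1 and Protocol 8.4.2.1, for the pooled two-stage population:
1. State that the count rule (≥ 11/44, ≥ 5/41) is the basis of the conclusion.
2. Beside Clopper-Pearson, report a 90% exact interval by stage-wise ordering, identified as the one that matches the test.
3. Label the pooled Clopper-Pearson interval as unadjusted for the two-stage design.
4. State that the stage-wise interval assumes the Stage 1 rule was followed on the interim responder count and does not model the randomized exit. If Stage 2 opens despite ≤ 3/19 or ≤ 1/21, or Stage 1 responders are added after the interim analysis, rely on the unadjusted interval.
5. Align the Synopsis level (95%) with Protocol 8.4.2.1 and SAP 7.5.1 (90%).

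The cost is a few sentences and a short program, with no change to conduct, sample size or decision rules. The stage-wise upper limit at the cut-off is wider by 39.43 − 37.97 = 1.46 points (SCLC) and 24.78 − 23.95 = 0.83 points (PAC). Its 90% guarantee is for the whole design; its lower coverage given continuation is why Clopper-Pearson should stay in the report.

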7.5.2 Overall Survival

OS will be estimated using KM methodology. Median values along with two-sided 95% CIs will be calculated. KM based OS rates at 3, 6, 9, 12, 18, and 24 months will be estimated and associated two-sided 95% CIs will be provided.

7.5.3 Progression-free Survival

PFS will be estimated using KM methodology. Median values along with two-sided 95% CIs will be calculated. KM based PFS rates at 3, 6, 9, 12, and 18 months will be estimated and associated two-sided 95% CIs will be provided.

The following information will also be summarized:

- Number and type of events (progression: RECIST 1.1 or clinical, death),
- Number of subjects censored on first dosing date (number with no baseline tumor assessment and no death, number with no on-study tumor assessment and no death)

- Number of subjects censored on date of last tumor assessment on-study (number received subsequent anti-cancer therapy, still on-treatment, in follow-up, off study [lost to follow-up, withdraw consent, other]).

7.5.4 Duration of Objective Response

Duration of response will be estimated using KM methodology for subjects who achieve PR or CR. Median values along with two-sided 95% CIs will be calculated.

For the responders only, the time course of the following events of interest will graphically be displayed (swimmers plot): tumor response, progression, last dose received and death.

7.5.5 Disease Control Rate

Analyses on disease control rate will be similar to the ones conducted on the ORR.

7.5.6 Magnitude of Reduction in Tumor Volume

The magnitude of reduction in tumor volume will be summarized descriptively using the following subject-level graphics:

- A bar plot (waterfall plot) showing the best reduction in target lesion (excluding assessment after PD and assessments after start of subsequent anti-cancer therapy).
- A plot (spider plot) of individual time course of tumor burden change.

7.5.7 Subsequent Therapy

The number of subjects with any of the following subsequent cancer therapy will be summarized:

- Radiotherapy,
- Surgery,
- Systemic cancer therapy.

The number of subjects with any allowed on-treatment radiotherapy or surgery will also be reported. Systemic cancer therapy will further be reported by therapeutic class and generic name.

A supportive listing will be provided.

7.6 Safety

Dose limiting toxicities will specifically be reported for the DLT Evaluation period. Other safety parameters will be reported according to the different phases of the trial. These parameters will consist of the incidence of deaths, adverse events, serious adverse events, adverse events leading to discontinuation, adverse events leading to dose modification, select adverse events, IMAEs, other adverse events of special interest, ECGs and specific laboratory abnormalities (worst grade) for each cohort.

For the Dose Evaluation Phase, safety parameters (excluding DLTs) will be summarized by cohort using the All Dose Evaluation Treated Subjects population.

For the Dose Expansion Phase, safety parameters will be summarized by cohort using the All 2-stage Including DLT Treated Subjects population.

For the Dose Evaluation Phase, if more than one cohort is to be reported pooled data across cohorts will also be presented.

7.6.1 DLT Evaluation Period / Maximum Tolerated Dose

During the DLT Evaluation period, data and Study Team considerations that led to the determination (or not) that the dose levels of 200mg and/or 400mg and/or 800 mg and/or 1600 mg weekly are tolerable and can be used during the Dose Evaluation Phase will be described in-text. This will be based on the incidence of DLTs during the first 6 weeks of treatment with both agents for the DLT-evaluable Subjects but other available safety and efficacy data may also be considered.

7.6.2 Deaths

The number of deaths and primary reason for death will be summarized for the following:

- All deaths,
- Deaths within 30 days of last dose,
- Deaths within 100 days of last dose.

Listing of deaths will be provided. In addition, to supply some safety information in subjects that were not treated, listing on deaths will be provided considering only the subjects who never started treatment.

7.6.3 Serious Adverse Events

For SAEs the following will be summarized:

- Overall summary of SAEs by worst CTC grade (grade 1, 2, 3, 4, 5, unknown) presented by SOC/PT,
- Overall summary of drug-related SAEs by worst CTC grade (any grade, grade 3-4, grade 5) presented by SOC/PT,

The analysis will be conducted using the 100-day safety window.

Listing of SAEs will be provided. In addition, to supply some safety information in subjects that were not treated, listing on SAEs will be provided considering only the subjects who never started treatment.

7.6.4 Adverse Events Leading to Discontinuation of Study Therapy

For AEs leading to discontinuation the following will be summarized:

- Overall summary of AEs leading to discontinuation by worst CTC grade (any grade, grade 3-4, grade 5) presented by SOC/PT,

- Overall summary of drug-related AEs leading to discontinuation by worst CTC grade (any grade, grade 3-4, grade 5) presented by SOC/PT,

The analysis will be conducted using the 100-day safety window.

Listing of AEs leading to discontinuation will be provided.

7.6.5 Adverse Events Leading to Dose Modification

Dose modification consists of dose delay of either drug and the following will be summarized:

- Overall summary of AEs leading to study therapy dose delay by worst CTC grade (grade 1, 2, 3, 4, 5, unknown) presented by SOC/PT.

The analysis will be conducted using the 100-day safety window.

Listing of AEs leading to study therapy dose delay will be provided.

7.6.6 All Adverse Events

For AEs the following will be summarized:

- Overall summary of any AEs by worst CTC grade (grade 1, 2, 3, 4, 5, unknown) presented by SOC/PT,
- Overall summary of any AEs by worst CTC grade (any grade, grade 3-4, grade 5) presented by SOC/PT,
- Overall summary of drug-related AEs by worst CTC grade (any grade, grade 3-4, grade 5) presented by SOC/PT,
- Overall summary of any non-serious AEs presented by SOC/PT. For the Dose Evaluation Phase, only the population of All Dose Evaluation Treated Subjects will be used.
- Overall summary of late-emergent drug-related AEs by worst CTC grade (grade 1, 2, 3, 4, 5, unknown) presented by SOC/PT,
- Overall summary of any AEs that required IMM by worst CTC grade (any grade, grade 3-4, grade 5) presented by SOC/PT.

The analyses will be conducted using the 100 days safety window.

Listing of AEs and listing of AEs requiring concomitant IMM will be provided.

